7.4 Safety³²

7.4.1 Adverse events

7.4.1.1 Definitions

7.4.1.1.1 Adverse event

In a clinical study, an AE is any untoward medical occurrence (i.e. any unfavorable and unintended sign [including abnormal laboratory findings], symptom or disease) in a subject or clinical investigation subject after providing written informed consent for participation in the study. Therefore, an AE may or may not be temporally or causally associated with the use of a medicinal (investigational) product or device.

7.4.1.1.1.1 Adverse device effect (ADE) - *amended*

An AE related to the use of Essure or NovaSure, including AEs resulting from insufficient or inadequate instructions for use, deployment, implant (placement), installation or operation or any malfunction of the investigational medical device, use error or from intentional misuse of the medical device.³³

7.4.1.1.1.2 Unanticipated adverse device effect (UADE)³⁴ - *amended*

A serious adverse effect is considered unanticipated if by its nature, incidence, severity or outcome it has not been identified in the IFU.

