7.4.1.3 Assessments and documentation of adverse events³⁸ - amended

Investigators must collect all AEs for each subject from the time of signing of the informed consent through the end of subject study participation, whether or not deemed related to the investigational device or procedure. All AE data will be recorded on the CRFs as well as documented in the subject's medical record and study source documents.³⁹

All SAEs and SADEs will be followed until the event has subsided or, in case of permanent impairment, until the event stabilizes and the overall clinical outcome has been ascertained.

Investigator must determine whether adverse event meets the definition of a serious adverse event; if so, it must be reported as required by Section 7.4.1.1.

Any SAE or incident will be reviewed and processed by the sponsor according to all applicable regulations.

Investigators must document all device failures, malfunctions and use errors, including the assessment of whether the event is considered an incident (ADE) using the Device Malfunction and Failure CRF.

Because an approved device will be used for the placement procedure, any device malfunctions will be reported to the sponsor's Product Surveillance department. Device malfunctions will not be analyzed as part of this study as the placement procedure and devices are not being evaluated.

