4.3 Handling of Missing Data

In order to achieve the goal of a well conducted clinical trial according to Good Clinical Practice (GCP), every effort will be made to collect all data. i.e., if a subject misses a

scheduled assessment, the site personnel will contact the subject and request her to come to the clinic for a visit. However, despite best efforts, it may be inevitable that missing or incomplete data are reported. Except as noted below, missing data will not be estimated or imputed.

General rules

When appropriate, the following rules will be implemented so as not to exclude subjects from statistical analyses due to missing or incomplete dates:

Table 1 - Imputation rules for missing adverse event start and stop dates

Scenario		
Start date	Stop date	Imputation rule
Partially Missing	Complete	
Imputation of start date:
 
A. If partial date has day and month missing: If the year is same as the year of the NovaSure EA procedure, then the day and month of the NovaSure EA procedure will be assigned to the missing fields If the year is prior to the year of the NovaSure EA procedure, then December 31 will be assigned to the missing fields. If the year is after the year of the NovaSure EA procedure, then January 01 will be assigned to the missing fields.
 
Note: if NovaSure EA procedure date is missing, then there is no need to impute the date as the AE is not treatment emergent.
 
B. If partial date has missing day only: If the month and year are same as the year and month of the NovaSure EA procedure, then the day of the NovaSure EA procedure will be assigned to the missing day.

		
If the month and year are before the year and month of the NovaSure EA procedure, then the last day of the month will be assigned to the missing day.
 
If the month and year are after the year and month of the NovaSure EA procedure, then the first day of the month will be assigned to the missing day.
 
If the imputed event start date (after A or B above) is after the event stop date, the start date will be imputed to be equal to the stop date.

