6.2.2 Secondary Endpoint Analyses

The secondary endpoint in the PAS is the incidence of adverse events when NovaSure EA is performed in the presence of Essure micro-inserts. There is no specific study hypothesis. Instead, the safety profile will be analyzed using summary statistics on the Safety Cohort as described in Section 6.3.

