6.3.1 Adverse Events

All AEs will be coded using MedDRA.

Frequency tables showing an overall summary of the number of events (where possible) and the number of subjects with AEs by system organ class (SOC) and preferred term (PT) will be given for the following types of AEs:

- All AEs
- AEs (possibly, probably, definitely) related to:
 - Essure device
 - NovaSure device
 - NovaSure procedure
 - Pre-existing condition
- AEs by intensity (mild, moderate, severe)
- AEs by outcome

- AEs of special interest
 - Defined as follows (updated annually by Medical Experts):

AE of Special Interest	Description	AEDECOD (PT)	AELLT
Abnormal Uterine Bleeding	Set to Y if AEDECOD equal to any of values in Column C:	Dysfunctional uterine bleeding	
		Genital hemorrhage	
		Genital haemorrhage	
		Menometrorrhagia	
		Menorrhagia	
		Metrorrhagia	
		Polymenorrhoea	
		Uterine hemorrhage	
		Uterine haemorrhage	
		Vaginal hemorrhage	
		Vaginal haemorrhage	
		Amenorrhea	
		Amenorrhoea	
		Hypomenorrhea	
		Hypomenorrhoea	
		Oligomenorrhea	
		Oligomenorrhoea	
		Bleeding anovulatory	
		Menstrual disorder	
Menstruation delayed			
Menstruation irregular			
Lower Abdominal Pelvic and Back Pain	Set to Y if AEDECOD='Back pain' and AELLT='Low back pain', otherwise set to Y if AEDECOD equal to any of values below:	Back pain	Low back pain
		Abdominal pain	
		Abdominal pain lower	
		Abdominal tenderness	
		Abdominal discomfort	
		Incision site pain	
		Implant site pain	
		Medical device discomfort	
		Medical device pain	
		Medical device site discomfort	
		Medical device site pain	
		Suprapubic pain	
		Visceral pain	
		Post ablation tubal ligation syndrome	
		Pubic pain	

		Groin pain	
		Genito-pelvic pain/penetration disorder	
		Uterine cervical pain	
		Ovulation pain	
		Pelvic pain	
		Pelvic discomfort	
		Dyspareunia	
		Adnexa uteri pain	
		Uterine tenderness	
		Uterine pain	
		Uterine spasm	
		Dysmenorrhoea	
		Menstrual discomfort	
		Premenstrual cramps	
Perforation	Set to Y if AEDECOD equal to any of values in Column C:	Fallopian tube perforation	
		Uterine perforation	
Upper genital tract infections	Set to Y if AEDECOD equal to any of values in Column C:	Endometritis	
		Salpingitis	
		Salpingo-oophritis	
		Pelvic inflammatory disease	
Expulsion or migration or unintentional removal of Essure inserts	Set to Y if AEDECOD equal to any of values in Column C:	Device dislocation	
		Device expulsion	
		Unintentional medical device removal	

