Potential allergy/hypersensitivity to Essure inserts	Set to Y if AEDECOD equal to any of values in Column C:	Allergy to animals	
		Allergy to chemicals	
		Allergy to metals	
		Hypersensitivity	
		Multiple allergies	
		Pruritus	
		Rash	
		Rash pruritic	
		Seasonal allergy	
		Urticaria	
Auto-immune	Set to Y if AEDECOD equal to any of values in Column C:	Autoimmune disorder	
		Autoimmune thyroiditis	
		Multiple sclerosis	
		Multiple sclerosis relapse	
		Rheumatoid arthritis	

- AEs occurring in at least 1% of subjects

The same AE tables listed above will be repeated for treatment-emergent serious AEs, except for AEs of special interest.

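### SAP 6.3.1 puts no onset limit on the AE tables but limits the serious-AE tables to treatment-emergent events, a term the SAP never defines

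*SAP*

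**What the plan says.** The protocol starts the AE clock at consent. Section 7.4.1.1.1 defines an AE as an untoward occurrence "after providing written informed consent for participation in the study", and section 7.4.1.3 states: "Investigators must collect all AEs for each subject from the time of signing of the informed consent through the end of subject study participation". Table 7–1 places consent at the screening visit, up to 30 days before NovaSure on Day 0.

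SAP 6.2.2 defines the endpoint that these data serve: "The secondary endpoint in the PAS is the incidence of adverse events when NovaSure EA is performed in the presence of Essure micro-inserts". It refers to SAP 6.3 for the analysis, as summary statistics on the safety cohort.

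SAP 6.3.1 says that "the number of subjects with AEs by system organ class (SOC) and preferred term (PT) will be given for the following types of AEs". The types are all AEs, AEs by relatedness, by intensity and by outcome, AEs of special interest, and AEs in at least 1% of subjects. None has an onset condition. The section closes with: "The same AE tables listed above will be repeated for treatment-emergent serious AEs, except for AEs of special interest".

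The only other use of the term in the SAP is a note in Table 1 of section 4.3: "if NovaSure EA procedure date is missing, then there is no need to impute the date as the AE is not treatment emergent".

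**The concern.** The AE tables and the serious-AE tables are presented as the same displays on nested sets of events, but the plan selects their events by different rules. Two consequences follow from the text as it stands.

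- The endpoint concerns AEs when NovaSure is performed, yet events that began before NovaSure enter the tables that report it. The special-interest list shows how this could happen: it includes bleeding and pelvic-pain terms, and every woman enters the study with menorrhagia. A worsening recorded between consent and ablation would be counted there.
- The serious-AE tables may not be a subset of the AE tables in the way a reader expects. A reader who compares the two could find a serious event in one and not in the other, with no rule in the SAP to explain it.

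Because the term is undefined, the programmer has to choose the start of the treatment-emergent period. That choice also decides how to treat a woman in whom NovaSure was attempted but who has no procedure date.

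**Working it through.** The plan states no figure on this point, so the check is mainly of the text.

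**Does any other section supply the missing filter?**

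- *Analysis set (SAP 5).* The safety cohort contains women who consented and in whom NovaSure was attempted. This selects women, not their events. Screening failures drop out, but a cohort member's events before NovaSure stay in.
- *Day 0 check (protocol 7.1.2.2).* Staff confirm that no AE has occurred since screening. The section does not say what happens to an event that has occurred, or whether it is analysed.
- *Date rules (SAP 4.3).* These expect events before NovaSure. For a start date with day and month missing: "If the year is prior to the year of the NovaSure EA procedure, then December 31 will be assigned to the missing fields". The result always precedes the procedure. The rules supply dates; they do not say which tables use them as a filter.

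No section supplies it.

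**Tracing two cases through the tables**

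| Output | Serious event after consent, before NovaSure | Serious event after an attempt, no procedure date on record |
|---|---|---|
| All AEs, intensity, outcome (6.3.1) | counted | counted |
| Special interest (6.3.1) | counted if the term is listed | counted if the term is listed |
| At least 1% (6.3.1) | contributes | contributes |
| Serious AEs (6.3.1) | not counted | not counted, by the note in 4.3 |
| ADEs that are SAEs (6.3.1.1) | counted if at least possibly device- or procedure-related | counted if at least possibly device- or procedure-related |

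SAP 6.3 also lists SAEs among the safety variables without an onset limit. The second case can arise because SAP 5 counts a woman as attempted if she comes to the site intending to have the procedure. The documents do not say whether a procedure date is recorded for her.

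**Size (illustration only)**

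Share of observed time before NovaSure = 30/(30 + follow-up days), with the full 30-day window and a constant AE rate:

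- three years: 30/(30 + 1,095) = 2.7%
- final call 28 days early or late: 30/(30 + 1,067) = 2.7%; 30/(30 + 1,123) = 2.6%
- a woman who leaves at one year: 30/(30 + 365) = 7.6%

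The documents give no AE rate. For assumed rates λ per woman-year, the expected number of 220 women with at least one event in a 30-day window is 220 × [1 − exp(−λ × 30/365.25)]:

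| Assumed λ | Women of 220 |
|---|---|
| 0.25 | 4.5 |
| 0.5 | 8.9 |
| 1 | 17.3 |
| 2 | 33.3 |

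For the 1% display, 1% of 220 is 2.2, so three women put a term on the list; with a cohort of 200, two would. The size of the safety cohort is not known, and 220 is the enrolment minimum.

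**The case against.** The strongest reply is that this is a word left out and not a choice of analysis. A collection window is not an analysis window. The date rules in SAP 4.3 cover AEs generally and are keyed to NovaSure, and a count by SOC and PT needs no onset date unless onset is a filter. The serious tables are also described as a repeat of the same tables. Treatment emergence may therefore have been meant throughout. This is plausible, so a reader should not infer that the SAP deliberately counts every event from consent; it nowhere says so. But the date rules do not settle the intent, because the serious-AE filter alone would require them. A programmer who follows the text still gets unfiltered AE tables.

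A second reply is that events which cannot be due to NovaSure are already separated. SAP 6.3.1 has separate tables for relation to the Essure device, the NovaSure device, the NovaSure procedure and a pre-existing condition. An event before NovaSure should not be rated NovaSure-related. This stands: the documents do not support the inference that NovaSure-attributed incidence is distorted. What remains affected are the all-causality, intensity, outcome, special-interest and 1% tables.

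Third, the endpoint is descriptive, with no hypothesis, and the 1% list is only a display cut-off. This also stands, and it limits the importance of the point.

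**Conclusion.** The inconsistency is in the current SAP text and no other section resolves it. As written, events before NovaSure enter the AE tables for the secondary endpoint, and a serious event in that window would be among all AEs but absent from the serious-AE tables of 6.3.1.

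The effect is probably small. The 2.7% figure assumes a constant rate, the full 30-day window and complete three-year follow-up. A reader might take it as an upper limit, but it is not one: dropout raises the share, and clustering of events around the procedure lowers it. A reader might also infer that the tables will fail to reconcile. They do so only if a cohort member has a serious event before NovaSure, or a serious event with no procedure date on record, and the documents give no basis for estimating how often that happens. 

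No success criterion depends on these tables. In this context, pre-exposure means before NovaSure only, since Essure is already in place at consent.

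**What to change.** - Define treatment-emergent once in the SAP: onset on or after the NovaSure procedure, or on or after the attempt date where no procedure date exists. A filter on the procedure date alone would not be enough, because attempted women in the safety cohort could lose their events. Bring the note in Table 1 of SAP 4.3 into line.
- Apply the definition to both the AE and the serious-AE tables of 6.3.1.
- State whether it applies to the ADE tables of 6.3.1.1.
- List all AEs and SAEs from consent to NovaSure separately, with their Essure relatedness.

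The cost is a short SAP definition, a filter and one listing; no new data are needed. The drawback is that Essure-related events before NovaSure move from the tables to the listing, which is why the listing should carry the Essure causality entry.

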7.4.1.1.5 Important Medical Events and events of special interest - amended

The Important Medical Events (IME) list is developed and published by European Medicines Evaluation Agency (EMA) (<http://eudravigilance.ema.europa.eu/human/textforIME.asp>). All AEs reported in this study will be reviewed against the most current IME list periodically, and any events that are contained on the IME list will be specifically reviewed and the Investigator will be asked to review and confirm whether or not the event meets the criteria for seriousness in his/her opinion. In addition, the following events of special interest will be closely reviewed by the sponsor's study medical expert:

- Perforations of the uterus, cervix or fallopian tubes.³⁷
- Upper genital tract infections (for example: endometritis, salpingo-oophoritis, salpingitis).
- Expulsion or migration of Essure inserts.
- Potential allergy/hypersensitivity to Essure inserts (for example: itch [pruritus], rash, hives [urticaria], facial edema, angioedema, allergy to metals).³⁷

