Because this is a PAS, the Essure System is subject to Medical Device Reporting (MDR) regulations. The sponsor will review all serious adverse events and unanticipated adverse device effects and determine their reportability to FDA according to 21 Code of Federal Regulations 803 "*Medical Device Reporting*" Reporting MDRs to FDA is required when the sponsor becomes aware of information that reasonably suggests that a marketed device has or may have caused or contributed to a death, serious injury or long-term pain necessitating surgical intervention, or has malfunctioned, and that the device or a similar device marketed by the manufacturer would be likely cause or contribute to a death or serious injury if the malfunction were to recur. In the event information is received that the NovaSure System may have caused or may have contributed to a death or serious injury, the sponsor will notify the complaint handling function of the manufacturer of the device (Hologic, Inc.).

Sponsor's notification of the investigational site

The sponsor will inform all investigational sites about reported relevant events (e.g. SAEs incidents, UADEs, device failures, device malfunctions) according to all applicable regulations.

If the adverse event is the result of an unanticipated adverse device effect, the investigator must report it to the sponsor within 3 working days after the investigator becomes aware of the event.⁴¹ The investigator will send to the sponsor all pertinent paperwork (discharge summaries, office notes, etc.) within 5 working days.

Reports relating to the subject's subsequent medical course must be submitted to the sponsor until the event has subsided or, in case of permanent impairment, until the event stabilizes and the overall clinical outcome has been ascertained. The investigator must report it to the Ethics Committee / IRB within the required time frame.

⁴¹ Wording modified per Amendment 6.

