6.3 Safety

The safety variables to be investigated in this study include the following:

- Adverse Events
 - Adverse events related (an AE that is at least possibly related to the Essure or NovaSure device/procedure) to Essure and/or NovaSure
 - Adverse events of special interest
 - Most common AEs ($\geq 1\%$)
- Serious Adverse Events (SAE)

- Most common SAEs ($\geq 1\%$)
- Device events for Essure and/or NovaSure
 - Device events leading to AEs
 - Device events that resulted in SAEs
 - Device events that could lead to SAEs
- Device removals
 - Number of subjects with removals
 - Removal procedures – days from last insert procedure to removal procedure, removal intended, primary reason for intentional device removal, procedures performed at time of device removal, number of devices removed per procedure
 - Essure inserts removed – insert location, complete device removal, device removed intact

The safety profile will be analyzed using summary statistics on the Safety Cohort.

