6.3.1.1 Adverse Device Events

All adverse device events that are also adverse events constitute adverse device effects (ADEs). ADEs are defined as AEs that are at least possibly related to the Essure or NovaSure device/procedure)

All adverse device effects (ADEs) will be summarized for the primary safety cohort. All ADEs will be coded using MedDRA.

Frequency tables showing an overall summary of the number of events (where possible) and the number of subjects with ADEs by system organ class (SOC) and preferred term (PT) will be given for the following types of ADEs:

- All adverse device events
- Adverse device events leading to AEs
- ADEs that are serious adverse events (SAEs)
- Adverse device events that could lead to SAEs
- Adverse device events by category (device deficiency, device failure, device malfunction, medical device report (MDR) reportable event, important medical events and events of special interest, unknown, and other)

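### The special-interest table is not repeated for serious AEs, so no planned table counts the women with at least one serious event in each category

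*SAP*

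**What the plan says.** SAP 6.3.1 lists the AE tables: all AEs, AEs by relationship, by intensity and by outcome, AEs of special interest, and AEs in at least 1% of subjects. For each type, events are counted where possible, and "the number of subjects with AEs by system organ class (SOC) and preferred term (PT) will be given".

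The special-interest categories are defined by flags. A record is set to Y if its preferred term is on the category's list; for back pain the lowest-level term must also be low back pain. There are seven categories: abnormal uterine bleeding; lower abdominal, pelvic and back pain; perforation; upper genital tract infection; "Expulsion or migration or unintentional removal of Essure inserts"; potential allergy or hypersensitivity; and auto-immune.

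The section closes with: "The same AE tables listed above will be repeated for treatment-emergent serious AEs, except for AEs of special interest."

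Protocol 7.4.1.1.5 has a shorter list of four types (perforation, upper genital tract infection, expulsion or migration, and allergy) and says that "the following events of special interest will be closely reviewed by the sponsor's study medical expert".

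**The concern.** The categories exist because one kind of harm can be coded under many terms. The SAP uses the grouping for AEs as a whole and sets it aside for the serious subset, where counts are smallest and splitting over terms obscures most. It gives no reason.

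Adverse event data are the only secondary endpoint (SAP 3.2), and SAP 6.2.2 analyses them by summary statistics without a hypothesis. The tables are therefore the safety result. A reader who asks how many women had a serious event of a given special-interest type would find rows for single terms but no answer.

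**Working it through.** The documents give no figure on this point to reproduce. The check is whether any planned output contains the count, and if not, whether it can be derived.

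**1. Entries per category, counted from the table in SAP 6.3.1**

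| Category | Entries |
|---|---|
| Abnormal uterine bleeding | 21 |
| Lower abdominal, pelvic and back pain | 29 |
| Perforation | 2 |
| Upper genital tract infections | 4 |
| Expulsion, migration or unintentional removal | 3 |
| Allergy/hypersensitivity | 10 |
| Auto-immune | 5 |
| Total | 74 |

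The bleeding list holds six pairs of US and UK spellings, so it has 21 − 6 = 15 distinct terms.

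**2. Planned outputs that include serious or special-interest events**

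| Output | Why it does not give the count |
|---|---|
| All serious AEs, and the repeats by relationship, intensity and outcome (6.3.1) | Subjects by organ class and preferred term, not by category |
| Special-interest table (6.3.1) | Covers all AEs together; not repeated for serious ones |
| Device effects that are serious (6.3.1.1) | By organ class and preferred term; related events only |
| Device events by category (6.3.1.1) | Pools important medical events with special-interest events; split neither by type nor by seriousness |
| Device removals (6.3) | Subjects counted, but not by seriousness |
| Listing (6.3.2) | Pregnancies only |

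None gives the number of women with a serious event per category.

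**3. Can it be derived from the preferred-term rows?**

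Let n₁, …, n_k be the numbers of women with a serious event under each of the k terms of a category. The number of women with at least one satisfies

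max(n₁, …, n_k) ≤ women ≤ n₁ + … + n_k.

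The upper bound is reached only if no woman has two terms, and the lower only if every woman is already in the largest row. In a hypothetical case with counts 3, 2 and 2, the bounds are 3 and 3 + 2 + 2 = 7. On 220 women, the minimum enrolment, that is 3/220 = 1.4% to 7/220 = 3.2%.

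Organ-class rows do not settle it. They count subjects over every term in the class, and the SAP does not tie any category to a single class.

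**4. The low-back condition**

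Back pain enters the pain category only when the lowest-level term is low back pain. A table by organ class and preferred term does not display that level. If serious back pain occurs, a reader cannot tell which of those women belong in the category, so even the bounds in step 3 become uncertain.

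**The case against.** The strongest reply is that the exception drops a table layout, not events. That is correct. A reader might infer that serious special-interest events go unreported. The SAP does not support this: they remain in the all-serious-AE table with subject counts, and again by relationship, intensity and outcome. Related ones also appear among the serious device effects.

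A reader might also infer that a serious cluster could be hidden because each term falls below the 1% line for common serious AEs (1% of 220 is 2.2, so 3 women). This does not follow either, because the all-serious-AE table has no cut-off and every term gets a row. How often a term would reach 1% depends on how events spread over terms, and the documents say nothing about that.

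Three further limits stand:

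- Fragmentation differs by category. Insert events have only 3 terms, so wide scatter cannot be claimed for them.
- The existing special-interest table covers all AEs, serious ones included. It is not a table of non-serious events.
- Pain and bleeding are special-interest categories in the SAP but are not among the four types in Protocol 7.4.1.1.5. The phrase "serious injury or long-term pain necessitating surgical intervention" in Protocol 7.4.1.4 describes when device reports go to the regulator; it does not define an analysis category.

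Finally, detection of serious events does not rest on this table. Protocol 7.4.1.4 requires serious AEs to reach the sponsor within 24 hours and the sponsor to review them all for reportability. The study is single-arm, so there is no comparator for an excess.

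None of this supplies the missing count, and nothing in the documents argues against producing it.

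**Conclusion.** The point holds as a limited reporting gap. Serious events are tabulated by organ class and preferred term, but no planned table gives the number of women with at least one serious event per special-interest category. That number cannot be recovered exactly from what is planned. The gap amounts to seven rows of one table.

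The conclusion rests on two readings. The first is that the exception means the table is not repeated, which is the natural sense of the sentence. The second is that the special-interest table carries a count per category. The flag definitions imply this, although the general lead-in mentions only organ class and preferred term. How far the term rows would mislead depends on how many women have more than one listed term, which cannot be known in advance; the 3-to-7 range is an illustration, not a forecast.

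No success criterion, error rate, power figure or clinical rule is affected.

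**What to change.** In SAP 6.3.1, delete the final clause of the sentence on serious AEs, so that the special-interest table is repeated for treatment-emergent serious events like the others. State its content explicitly: on the Safety Cohort, for each category, the number and percentage of women with at least one serious event, each woman counted once, with the number of events alongside. The flags, including the low-back rule, apply unchanged.

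The cost is one further run of a table whose definitions already exist. The category flags and the seriousness classification are already planned, and no new data are needed.
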